## PROTOCOL SYNOPSIS

**Gilead Sciences, Inc.**  
**[name]**  
**[name] USA**

---

Study Title:	A Phase 3, Randomized, Double-Blind, Placebo-Controlled Study Evaluating the Safety and Efficacy of Selonsertib in Subjects with Nonalcoholic Steatohepatitis (NASH) and Bridging (F3) Fibrosis
---------------------	---

---

IND Number:	125393
EudraCT Number:	2016-004374-18
Clinical Trials.gov Identifier:	NCT03053050

---

Study Centers Planned:	Approximately 460 centers globally
-------------------------------	------------------------------------

---

Number of Subjects Planned:	Approximately 800 subjects
------------------------------------	----------------------------

---

Target Population:	Males and non-pregnant, non-lactating females between 18 - 70 years of age with NASH and bridging fibrosis.
---------------------------	---

---

Duration of Treatment:	Subjects will be treated for up to 240 weeks.
-------------------------------	---

---

Duration of Study:	
Individual subject participation in the study can last up to 260 weeks, which includes an 8-week Screening period, a 240-week treatment period, a 4-week Follow-Up period and a Telephone Follow-Up visit 12 weeks after the Week 240 or Early Termination (ET) visit, as applicable.
 
The total study duration is anticipated to be approximately 7 years, including an enrollment period of approximately 2 years.

---------------------------	---

---

[figure not shown]
Objectives:	
The primary objective of this study is:
 

• To evaluate whether selonsertib (SEL, previously known as GS-4997) can cause fibrosis regression and reduce progression to cirrhosis and associated complications in subjects with NASH and bridging (F3) fibrosis

 
The secondary objective of this study is:
 

• To assess the safety and tolerability of SEL in subjects with NASH and bridging (F3) fibrosis

--------------------	--

---

**Study Design:**

This is a Phase 3, randomized, double-blind, placebo-controlled study evaluating the safety and efficacy of SEL in subjects with NASH and bridging (F3) fibrosis.

Subjects meeting the study's entry criteria will be randomly assigned in a 2:2:1 ratio to 1 of 3 treatment groups as shown in the figure below:

**Randomized Study Phase**

Randomization will be stratified by the presence or absence of diabetes mellitus (as determined by medical history or based on Screening lab values if previously undiagnosed [i.e. hemoglobin A1c (HbA1c)  $\geq$  6.5% or fasting plasma glucose  $\geq$  126 milligram/deciliter [mg/dL]) and by Enhanced Liver Fibrosis (ELF™) score  $\geq$  9.76 or  $<$  9.76 during Screening. Study drugs will be administered for up to a total of 240 weeks.

A key primary objective of this study is to prevent progression to cirrhosis and its complications. A composite of clinical events that constitute the clinical efficacy endpoint have been identified and include:

- 1) Progression to cirrhosis as defined by a liver biopsy showing F4 fibrosis according to the NASH Clinical Research Network (CRN) classification as assessed by the central reader
- 2) Events of hepatic decompensation including:
  - a) Clinically apparent ascites requiring treatment
  - b) Hepatic encephalopathy (HE) of Grade 2 or above (according to the West Haven criteria as defined in [Appendix 5](#)) requiring treatment

- c) Portal hypertension-related upper gastrointestinal bleeding identified by endoscopy and requiring hospitalization, including events of bleeding from esophageal varices, gastric varices, and portal hypertensive gastropathy
- 3) Liver transplantation or qualification for liver transplantation, defined as a Model for End-stage Liver Disease (MELD) score  $\geq 15$  on at least 2 consecutive occasions at least 4 weeks apart
- 4) All-cause mortality

Subjects who experience a confirmed hepatic clinical event prior to completing the Week 240 Visit of the Randomized Phase will be offered the option to rollover into an Open-Label (OL) Phase of the study. Each of the clinical events (except histologic progression to cirrhosis, all-cause mortality and liver transplantation) will require confirmation by a Hepatic Events Adjudication Committee. All deaths will be reviewed by this committee to determine if they are liver-related.

If a subject is clinically felt to have progressed to cirrhosis (e.g., based on the presence of new esophageal varices, changes in biomarkers [including, but not limited to, low serum albumin, high serum bilirubin, a low platelet count, prolonged INR, or elevated liver stiffness], or development of other clinical signs or symptoms of cirrhosis), the subject should undergo repeat liver biopsy for confirmation of progression to cirrhosis (F4 fibrosis as assessed by the central reader according to the NASH CRN classification) at the discretion of the primary investigator (PI).

Once the clinical event (except histologic progression to cirrhosis, all-cause mortality and liver transplantation) is confirmed by the Hepatic Events Adjudication Committee, the subject will no longer participate in the Randomized Phase and will be offered the option to receive SEL 18 mg in the OL Phase for a total treatment duration of 240 weeks inclusive of the Randomized Phase. Rollover into the OL Phase of the study must occur within 60 days of confirmation of the event. Subjects starting the OL Phase of the study will complete the same study procedures as during the Randomized Phase of the study, CCI

Hepatic clinical events will be adjudicated and deaths will be reviewed by the Hepatic Events/DILI Adjudication Committee only during the Randomized Phase of the study; potential DILI events and cardiovascular events including deaths will continue to be adjudicated in the OL Phase by the Hepatic Events/DILI Adjudication Committee and the Cardiovascular Events Adjudication Committee, respectively.

Cardiovascular events including cardiovascular death, myocardial infarction, stroke, hospitalization for unstable angina, hospitalization for cardiac failure, and coronary revascularization will be adjudicated by an independent Cardiovascular Events Adjudication Committee. Subjects experiencing a cardiovascular event will continue in the Randomized Phase and not rollover into the OL Phase. Cardiovascular events will be adjudicated during the Randomized Phase and the OL Phase of the study.

Diagnosis and  
Main Eligibility  
Criteria:

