#### 1.2.6.3. Safety Results

The frequency of AEs was similar for both treatment groups: 47 subjects (94.0%) and 49 subjects (94.2%) in the SEL + PRED and placebo + PRED groups, respectively. The frequency of treatment-related AEs was similar for both groups: 13 subjects (26.0%) and 14 subjects (26.9%) in the SEL + PRED and placebo + PRED groups, respectively. Adverse events leading to discontinuation of SEL or placebo were reported for 9 subjects (18.0%) in the SEL + PRED group and 4 subjects (7.7%) in the placebo + PRED group.

At the time of the data cutoff date of 16 February 2018, a total of 20 subjects had died: 14 subjects (28.0%) in the SEL + PRED group and 6 subjects (11.5%) in the placebo + PRED group. The majority of these deaths occurred after subjects had completed or prematurely discontinued study drug. Four deaths (2 in each group) occurred up to Day 28 (i.e., during the planned duration of treatment). Most deaths involved complications of severe alcoholic hepatitis, including infections.

The most commonly reported AEs in the SEL + PRED group were ascites and hyponatremia (each 16 subjects [32.0%]), hepatic encephalopathy (14 subjects [28.0%]), and edema peripheral (13 subjects [26.0%]). In the placebo + PRED group, the most commonly reported AEs were ascites (15 subjects [28.8%]), edema peripheral (11 subjects [21.2%]), and hepatic encephalopathy (10 subjects [19.2%]).

A greater percentage of subjects in the SEL + PRED group (25 subjects [50.0%]) experienced SAEs compared with the placebo + PRED group (21 subjects [40.4%]). The most common SAEs overall were hepatic encephalopathy, acute kidney injury, cellulitis, coagulopathy, hepatorenal syndrome, hyponatremia, and pneumonia. A greater percentage of subjects in the SEL + PRED group (12 subjects [24.0%]) experienced SAEs of infections compared with the placebo + PRED group (5 subjects [9.6%]), which included SAEs of brain abscess reported in 2 subjects in the SEL + PRED group at the same study site (PTs: brain abscess and fungal abscess central nervous system, 1 subject each).

Overall, rates of AEs were similar between subjects in the SEL + PRED and placebo + PRED groups. However, higher rates of serious infections and hyponatremia were seen in subjects with severe AH who received SEL + PRED compared with placebo + PRED.

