### 6.7. Open-Label Phase

Subjects who progress to cirrhosis on liver biopsy or experience a hepatic clinical event (refer to Section 3.2) prior to completing the Week 240 Visit of the Randomized Phase will be offered the option to rollover into an Open-Label (OL) Phase of the study. Each of the clinical events (except death and liver transplantation) will require confirmation by a Hepatic Events Adjudication Committee. All deaths will be reviewed by this committee to determine if they are liver-related.

Subjects who undergo liver transplantation are not eligible to participate in the OL Phase of the study and should discontinue from the study immediately. Subjects who have permanently discontinued study drugs are not eligible for the OL Phase of the study.

Once a clinical event (except histological progression to cirrhosis, death and liver transplantation) is confirmed by the Hepatic Events Adjudication Committee, the subject will no longer participate in the Randomized Phase and will be offered the option to receive SEL 18 mg in the OL Phase for a total treatment duration of 240 weeks inclusive of the Randomized Phase.

Rollover into the OL Phase of the study must occur within 60 days of confirmation of the event. Subjects starting the OL Phase of the study will complete the same study procedures as during the Randomized Phase of the study, CCI

. Hepatic clinical events will be adjudicated and deaths will be reviewed by the Hepatic Events/DILI Adjudication Committee only during the Randomized Phase of the study; potential DILI events and cardiovascular events including deaths will continue to be adjudicated in the OL Phase by the Hepatic Events/DILI Adjudication Committee and the Cardiovascular Events Adjudication Committee, respectively.

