#### **6.9. Assessments for Premature Discontinuation from Study**

Subjects prematurely discontinuing from the study should complete an ET visit within 30 days of last dose, a Follow-Up visit 4 weeks later, and a Telephone Follow-Up visit 12 weeks after the ET visit.

If a subject is lost to follow-up, survival data may be gathered from public records such as government census or death records (if permitted by local regulations) prior to the completion of the study.

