#### **6.11.13. Liver Biopsy**

All possible attempts should be made to acquire a liver biopsy specimen of at least 2.0 cm in length to ensure accurate staging of fibrosis and other histological lesions. A historical biopsy within 6 months of the Screening visit may be accepted as the Screening biopsy. The liver biopsy sample must be deemed adequate for evaluation by the central reader for inclusion.

Liver biopsies will be sent to a central laboratory and then will be read by a central reader. The central reader will read all Screening biopsies for eligibility. This assessment will include an assessment of the adequacy of the specimen as well as the fibrosis stage and a determination that the biopsy is consistent with NASH. Histology results from local readers will be collected, if available.

If the liver biopsy is deemed unacceptable by the central reader, it may be repeated. On-treatment liver biopsy results will be blinded to the investigator and subject unless the subject progresses to cirrhosis (F4 fibrosis). CCI

If a liver biopsy is performed per standard of care outside of protocol mandated assessments (e.g., to confirm clinical suspicion of progression to cirrhosis), all possible attempts should be made to submit the biopsy specimen to the central reader for evaluation. If progression to cirrhosis is confirmed by the central reader, the subject will be offered the opportunity to rollover into the OL Phase of the study.

Please refer to the Study Procedures Manual for additional information.

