#### **Clinical Efficacy Endpoint Analysis**

The clinical efficacy endpoint at Week 240 is EFS. EFS will be assessed by time to the first clinical event in the Randomized Phase. Differences in time to the first clinical events between each of the SEL arms and the placebo arm will be assessed using the stratified log-rank test. A sensitivity analysis of EFS that includes hepatic clinical events and liver-related death will also be performed. The clinical efficacy endpoint will only be evaluated at Week 240 for a SEL arm if the SEL arm demonstrates superiority over placebo for the primary efficacy endpoint at Week 48.

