3.2. Subject Grouping

For analyses based on the FAS, subjects will be grouped according to the treatment to which they were randomized. For analyses based on the Safety Analysis Set, subjects will be grouped according to actual treatment received. The actual treatment received will differ from the randomized treatment only when the actual treatment differs from the randomized treatment for the entire treatment duration. In this case, the actual treatment received is defined as the treatment received for the entire treatment duration.

For safety analyses, subjects will be grouped into the following:

Randomized Phase (only Randomized Phase data will be summarized for these groups)

- 1) SEL 18 mg: This group includes all subjects who received SEL 18 mg in the Randomized Phase.
- 2) SEL 6 mg: This group includes all subjects who received SEL 6 mg in the Randomized Phase.
- 3) SEL Pooled: This group includes all subjects who received SEL 18 mg or SEL 6 mg in the Randomized Phase.
- 4) Placebo: This group includes all subjects who received only placebo in the Randomized Phase.

Open-Label Phase (only OL Phase data will be summarized for this group):

OL SEL 18 mg: This group includes all subjects who received OL study drug.

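### No planned analysis clearly compares all-cause mortality to Week 240 by randomised arm once a subject has had a first hepatic event, and survival follow-up of those who then leave the study is not specified beyond about 12 weeks.

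*Protocol*

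**What the plan says.** **Leaving the randomised comparison.** The Protocol Synopsis, 3.3.1 and 6.7 state that after an adjudicated hepatic event "the subject will no longer participate in the Randomized Phase and will be offered the option to receive SEL 18 mg". Section 6.7 limits the rule: "Once a clinical event (except histological progression to cirrhosis, death and liver transplantation) is confirmed by the Hepatic Events Adjudication Committee". Biopsy-proven cirrhosis is therefore outside the exit sentence, but 6.11.13 adds: "If progression to cirrhosis is confirmed by the central reader, the subject will be offered the opportunity to rollover into the OL Phase".

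**Who cannot roll over.** Protocol 6.7: "Subjects who have permanently discontinued study drugs are not eligible for the OL Phase of the study". The same section bars transplant recipients from the OL Phase and has them leave the study at once.

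**After leaving the study.** Protocol 6.9 gives an ET visit, a visit 4 weeks later and a telephone contact at 12 weeks. Its only tracing clause is optional: "If a subject is lost to follow-up, survival data may be gathered from public records such as government census or death records".

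**Analysis.** Protocol 8.6.1: "EFS will be assessed by time to the first clinical event in the Randomized Phase". SAP 6 excludes data from the first OL dose onward from efficacy. For safety, SAP 3.2 heads the arm groups "Randomized Phase (only Randomized Phase data will be summarized for these groups" and puts everyone given OL drug into a single SEL 18 mg group. Protocol 8.8 also summarises OL safety over all rollovers together. SAP 7.1.6 puts every death seen in the study into a high-level summary by treatment group, and SAP 3 shows the initially assigned arm in listings.

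**The concern.** Safety is the secondary objective, and death is its least ambiguous outcome. A death that follows decompensation is not an EFS event, because the decompensation was the first event. If the subject has moved to the OL Phase, the death falls in a pooled group that mixes former placebo, 6 mg and 18 mg subjects. If the subject has left the study, the death may not be observed at all. The arm-level death count is thus cut off selectively at hepatic events. If SEL caused liver harm, some of the resulting deaths would drop out of the SEL count; if SEL worked, placebo would lose more.

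The sponsor has a reason to look. In its alcoholic hepatitis (AH) study (Protocol 1.2.6.3), deaths were more frequent on SEL plus prednisolone than on placebo plus prednisolone, and "The majority of these deaths occurred after subjects had completed or prematurely discontinued study drug".

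**Working it through.** **1. The plan's own rates (Protocol 8.10).** Arms of 320, 320 and 160; events by Week 240 of 30% on placebo and 16.3% on SEL; HR 0.50; dropout 20%.

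- HR check: ln(0.837)/ln(0.70) = 0.499, which reproduces the stated 0.50.
- First events: placebo 0.30 × 160 = 48; each SEL arm 0.163 × 320 = 52.2; total 48 + 2 × 52.2 ≈ 152, or 152/800 = 19%.
- With exponential dropout of 20% by Week 240, events per arm = N × λ/(λ+γ) × [1 − exp(−(λ+γ)T)], where γT = −ln 0.80 = 0.223, and λT = 0.357 (placebo) or 0.178 (SEL). This gives 43.3 and 46.9 per arm, total 43.3 + 2 × 46.9 ≈ 137 (17%).

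These are ceilings. They include first events that are deaths, which EFS already counts by arm, and cirrhosis found at the Week 240 biopsy, after which no follow-up to Week 240 remains.

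**2. Follow-up time after a first event.** With exponential event times and no dropout, the share of person-time to Week 240 is 1 − (1 − S)/(−ln S). Placebo: 1 − 0.300/0.357 = 16%. SEL: 1 − 0.163/0.178 = 8%. On the plan's assumptions the cut-off therefore removes about twice the share from placebo. Scheduled biopsies cluster the real event times, so this is rough.

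**3. Clinical hepatic events only.** Protocol 1.4.1 cites a natural-history cohort with 14% liver-related events in F3 over a median of 12.6 years. Assuming constant hazard: −ln(0.86)/12.6 = 0.0120 per year. Over 240 weeks (4.6 years): 1 − exp(−0.0120 × 4.6) = 5.4%, and 0.054 × 800 ≈ 43. That cohort's event definition differs from this trial's, and the figure assumes no treatment effect.

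**4. Deaths affected.** The documents give no post-event mortality, so these are assumptions. Suppose 50–100% of events leave time before Week 240 and 10–30% of those subjects die by then.

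| Base | Low | High |
|---|---|---|
| 152 (ceiling) | 0.5 × 152 × 0.10 ≈ 8 | 152 × 0.30 ≈ 46 |
| 43 (clinical only) | 0.5 × 43 × 0.10 ≈ 2 | 43 × 0.30 ≈ 13 |

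A flat 2–20% of 152 gives about 3 to 30, inside the same overall range.

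**5. AH study (Protocol 1.2.6.2 and 1.2.6.3).** Deaths 14/50 (28.0%) v 6/52 (11.5%), as stated: risk ratio 2.43 (95% CI 1.01 to 5.82), Fisher p = 0.047. Two deaths per group fell by Day 28, leaving 12/50 (24.0%) v 4/52 (7.7%) afterwards, Fisher p = 0.030.

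**6. The two SAP sections side by side.** Section 7.1.6 opens by grouping subjects as in 3.2, and 3.2 keeps OL data out of the arm columns. Yet 7.1.6 also wants all study deaths in a by-treatment summary, in wording wider than the treatment-emergent rows above it. An OL death in a former placebo subject belongs under placebo on one reading and only in the OL group on the other. Neither section says which.

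**The case against.** Much can be said for the plan.

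- A reader might infer that nobody is traced after a hepatic event. The documents do not support that. Rollovers follow the same schedule for up to 240 weeks in total, and Protocol 7.3 requires deaths to be reported throughout the study and its follow-up. For them only the tabulation is in doubt.
- A reader might infer that post-event deaths are never shown by arm. That is also too strong, given SAP 7.1.6 and the listings by assigned arm. What stands is that the table is ambiguous, that a listing is not an analysis, and that neither recovers unobserved deaths.
- Not all 152 subjects leave arm-level follow-up. The exit sentence excludes biopsy cirrhosis. Those who accept rollover leave the arm-level safety data; the status of those who decline is unstated.
- Protocol 6.8 encourages subjects who stop treatment to attend to Week 240. It does not say how that fits with the exit rule.
- Hepatic harm itself is not hidden: decompensation is an EFS event compared by arm, and so is a death without an earlier event, on or off drug.
- The AH data are preliminary and come from severe disease treated with prednisolone. Most deaths involved complications of that disease, and alcoholic liver disease is excluded here. The diabetic kidney disease study had 1.2% deaths in both the placebo and pooled SEL groups (Protocol 1.2.4.2). The post hoc p-value is borderline. This is a reason to look, not evidence of harm in NASH.

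These points narrow the concern. They do not supply an arm-level mortality comparison that includes deaths after a first hepatic event.

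**Conclusion.** The concern holds in this limited form. No planned analysis clearly gives all-cause mortality to Week 240 by randomised arm including post-event deaths. SAP 3.2 and 7.1.6 conflict on where OL deaths go. Transplant recipients, and event subjects who decline or cannot enter the OL Phase and leave the study, have no specified survival follow-up beyond about 12 weeks after ET.

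At most about 152 of 800 subjects are involved (about 137 with dropout), and perhaps about 43 if only clinical hepatic events are counted. The deaths affected range from about 2 to 46, entirely on assumed post-event mortality. How many subjects would leave without entering the OL Phase cannot be estimated from the documents.

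It is tempting to call a comparison diluted by crossover conservative. For harm it is the reverse: every rollover receives SEL 18 mg, so the arms are pulled together and a real excess could be masked. The change is still worth making before the final analysis because it is cheap.

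**What to change.** 1. **SAP 3.2 and 7.1.6.** Add a safety summary of all-cause deaths by randomised arm, from randomization to each subject's scheduled Week 240 date, counting deaths in the OL Phase and after study exit: number, Kaplan-Meier estimate, and hazard ratio with confidence interval. Reconcile the two sections so that the arm to which an OL death is assigned is explicit.
2. **Protocol 6.7 and 6.9.** Obtain vital status at the scheduled Week 240 date for every randomised subject, whatever their event, OL, transplant or drug status, by telephone or the public records that 6.9 already allows, unless consent for this is withdrawn. State what follow-up applies to subjects who decline rollover, including those with biopsy cirrhosis, and reconcile this with 6.8.
3. **State the limits with the table.** Crossover to SEL 18 mg means that a null result is not reassurance about harm, and deaths may be few against a placebo arm of 160.

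**Cost.** One contact or records check for each subject who has left, plus one table and one figure. No visit or procedure is added. Consent wording must cover the check. The sponsor's pulmonary arterial hypertension study already counted deaths found at vital status checks (Protocol 1.2.5.2).
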